Vitamin A and D deficiencies are each associated with impaired innate and humoral immune responses and vulnerability to respiratory tract infectious diseases. Rates of vitamin A and D deficiencies or insufficiencies have skyrocketed in the United States, especially in the mid-south region. Animal studies have demonstrated that in vitamin deficient mice, antibody immune responses are poor toward influenza virus vaccine and are improved if a vitamin supplement is administered at the time of vaccination. The central hypothesis of this protocol is that vitamin supplements will enhance antibody responses toward an influenza virus vaccine in children. Children will be randomized using a stratified permuted block method to receive an influenza virus vaccine with vitamin A+D supplement or placebo. Participants will be stratified based on retinol binding protein (RBP) levels at screening, using a cut-off indicative of vitamin A insufficiency (<22,000 ng/ml). Co enrolled sibling participants will be first stratified by RBP levels, then siblings within a same stratum will be equally assigned to different arms to provide greater assurance of balanced treatment assignment. Children will be tested for vitamin levels and immune responses before and after influenza virus vaccinations to determine if vitamin supplementation improves the vaccine-induced antibody response.

Intervention: Children will be randomized to receive influenza virus vaccine plus vitamin A and D supplements (intervention) or Influenza virus vaccine plus matched placebo.

Brief Outline of Treatment Plan: Children between the ages of 2 and 8 years will be enrolled. All will receive two doses of an influenza virus vaccine administered at least 28 days apart. Vitamin levels and antibody responses toward the vaccine will be measured on days 0 (baseline levels), 28, and 56. Vitamins A + D will be orally administered at the levels of 20,000 IU and 2,000 IU respectively on the days of vaccinations for the children randomized to receive vitamin supplements. Parents will be asked to fill out diary cards to indicate food intake for children (intervention & control) over the study period along with an optional food frequency questionnaire given on day

Protocol MNEMONIC and Title: FLUVIT - A double-blind, randomized, placebo controlled study of antibody induction by vitamin supplementation at the time of influenza virus vaccinations in children

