Participants will be randomized to receive either influenza virus vaccine plus vitamins A and D supplements (n=40) or influenza virus vaccine plus matched placebo. Gummies for the intervention and control arm (placebo) will be provided in the same container by an unblinded pharmacist to maintain blinding. For the purposes of this study, Study Day 0 is defined for each participant as the day that the first influenza vaccine dose is administered. All participants will receive 2 doses of influenza virus vaccine at least 28 days apart.

Children will have the first influenza virus vaccine dose (dose 1) administered on day 0 of the trial, and the second dose (dose 2) administered 28 days later.

Vaccines will be administered by a technique consistent with the manufacturer's specification.

Participants will be observed for 30 minutes following vaccination. Participants will be given a food diary card to record their diet between the Day 0 and Day 56 study visits.

Blood serum samples will be collected from participants at Screening and prior to receiving the influenza virus vaccine on Day 28 as well as during their Day 56 follow-up visit.

Chewable Vitamin or Placebo Administration

Chewable Vitamin A & D3 or Placebo Gummy

The chewable gummy contains either Vitamin A (20,000 International Units) and Vitamin D3 (2,000 International Units) or matched placebo, which should be fully chewed under supervision of study staff with documentation in the participants research record and eMAR (electronic medical administration record). The chewable gummy should be administered prior to receiving influenza virus vaccine vaccination.

If participants have difficulty chewing the gummy, another option is to cut the chewable vitamin in half along score line for easier administration.

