6.2. Day 0 (Vaccine dose #1) Visit

For the purposes of this study, Study Day 0 is defined for each participant as the day that the first vaccine (Influenza virus vaccine) is administered.

Day 0 must be completed within 10 days of the screening assessment. If greater than 10 days passes, the participant must repeat the screening visit to confirm eligibility.

All Screening and Entry visit data must be collected prior to the receipt of vaccination and vitamin (A and D) dose #1. Vitamin or placebo chewable

gummy must be administered prior to influenza virus vaccine dose administration.

The following will be collected as a part of the Entry Visit:

- Chewable gummy (vitamin supplements or placebo depending on randomization) dose administration
- Administration of influenza virus vaccine Dose #1 for intervention and control group and observation in clinic 30 minutes post-vaccine administration
- Dispense food diary to control and intervention participants.
- Serum for vitamin studies
- Serum for immunologic studies

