6.3. Day 28 (Vaccine dose #2) Visit

The following will be completed:

- Interim medical history and medication use
- Laboratory evaluations
 - Serum for vitamin studies
 - Serum for immunologic studies
- Collection of food diary from participants
- Administration of influenza virus Vaccine Dose #2 to Intervention and Control group participants
- Administration of chewable gummy dose #2
- Dispense food diary to control and intervention participants.

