6.4. Day 56 Follow-Up Visit

The following will be completed:

- Interim Medical History and medication use
- Collect food diary from participants
- Laboratory evaluations:
 - Serum for vitamin studies
 - Serum for immunological studies
- At day 56, participants enrolled after approval of Revision 1.1, will be given the option to complete the Block food frequency questionnaire (FFQ). This questionnaire includes about 90 questions and asks about a child's "usual eating habits in the past 6 months." It takes a caregiver or interviewer approximately 30 minutes to complete. The food list was

developed from NHANES III dietary recall data. The nutrient database was developed from the USDA Nutrient Database for Standard Reference. Individual portion size is asked for beverages but not other foods. Dietary information obtained from this questionnaire is for exploratory purposes only.

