To assess the functional antibody response toward the influenza virus vaccine in the sera

Secondary analyses will examine sero-conversion defined as antibody HAI titers of $<1:20$ converting to $\geq 1:20$, or a four-fold increase in titer for participants with a starting titer of $\geq 1:20$. Sero-conversion rate will be estimated with proportion and 95% confidence interval for both groups, overall and by stratum. The rate difference will be described with point estimate and 95% confidence interval, overall and by stratum. Due to possible variation in virus strains and influenza virus vaccine compositions in different flu seasons, analyses by season will also be described.

Continuous titer values in both groups, overall or by stratum, will also be described and compared with point estimate along with 95% confidence intervals.

We will also apply generalized estimating equations (GEE) or mixed models to explore titer levels longitudinally.

Analysis of Exploratory Objectives

To describe the socio-demographic characteristics and nutritional diet among children participating in the trial.

Socio-demographic and dietary intake will be described with tables and descriptive statistics (frequency, proportion mean, standard deviation, median, range, etc...). The anticipated socio-demographic heterogeneity of participants may preclude further analysis, but if feasible, relationships between socio-demographic characteristics and dietary intake with outcomes will be examined.

To assess the feasibility of the food diary among healthy volunteers as measured by completion of the diary.

To assess the feasibility of the food diary among healthy volunteers, the proportion and 95% confidence interval of participants who complete and return the food diary will be calculated overall and at each visit time point.

To monitor serum Vitamin A and D levels at various time points.

Serum Vitamin A and D levels at screening, days 0, 28 and 56 will be monitored, plotted and described at each time point. Summary statistics, such as mean, standard deviation, median and range, will be provided for all time points. If feasible, paired comparisons and longitudinal modeling will be explored.

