APPENDIX I: SCHEDULE OF EVALUATIONS

Study Visit	Screening	1 st Vaccine Visit ^a	2 nd Vaccine Visit	Follow-Up Visit (Off-Study)	Early Discontinuation
Study Day (Window)	-10 ^a	0	28 (+3 days)	56 (+/- 7 days)	
Clinical Evaluations					
Informed Consent	X				
Randomization ^d		X			
Medical History	X	X	X	X	X
Current Medication Use	X	X	X	X	
Socio-Demographics Questionnaire	X				
Food Frequency Questionnaire				X	
Compensation (\$50)	X	X	X	X	X
Laboratory Evaluations					
Blood Sample Collection ^c	X	X	X	X	X
Vaccine and Vitamin Administration					
Vaccine Administration		X ^b	X ^b		
Vitamin A and D or Placebo Administration ^d		X	X		
Participant Diaries					
Food Diary		X	X		X

^a Day 0 (1st Vaccine Dose) must occur within 10 days of screening.

^b Participants will be observed for 30 minutes post-vaccination.

^c Serum for Vitamin and Immunologic Studies

^d Randomization must occur prior to initiating any Day 0 visit evaluations.

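### The confidence interval for food-diary completion counts children as independent, although co-enrolled siblings probably share the caregiver who returns the diary; the interval is likely to be somewhat too narrow

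*Combined protocol and SAP*

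**What the plan says.** Section 1.3 lists feasibility of the food diary, measured by its completion, as an exploratory objective. Section 11.4 gives the analysis: a proportion with a 95% confidence interval for "participants who complete and return the food diary will be calculated overall and at each visit time point". It names no split by arm and no adjustment for families.

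On who completes the diary, the synopsis says "Parents will be asked to fill out diary cards to indicate food intake for children (intervention & control) over the study period". Section 4.1 allows siblings to co-enrol and assigns those in the same RBP stratum equally to the two arms, in blocks of two.

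On timing, section 4.1 says "Participants will be given a food diary card to record their diet between the Day 0 and Day 56 study visits". The visit sections then set out the steps:

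- Day 0 (6.2): "Dispense food diary to control and intervention participants".
- Day 28 (6.3): "Collection of food diary from participants", and a second diary is handed out.
- Day 56 (6.4): "Collect food diary from participants".

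The corresponding row of Appendix I reads "Food Diary X X X". The three marks stand under Day 0, Day 28 and Early Discontinuation, and the Day 56 column is blank.

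**The concern.** Children aged 2 to 8 years do not return a diary by themselves; a caregiver does. If a family enrols two children, the two returns are likely to succeed or fail together, so the second child adds less than one child's worth of information. An interval that counts children as independent then claims more precision than the data hold.

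The plan recognises sibling dependence, but only under the primary objectives and only for the group difference. Its argument is that siblings are split between the arms. The diary proportion has no arm contrast, so that argument gives it no protection.

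What is at stake is limited: the stated precision of a feasibility rate that may guide whether a diary is used in a later, larger study.

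**Working it through.** **The plan's own figure.** There is none to reproduce. The documents give no expected return rate, target precision or threshold for the diary.

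**Inputs.** From the documents: 80 evaluable and 100 enrolled participants (section 11.3), and a per-child proportion with a 95% interval (section 11.4). Assumed: siblings come in pairs; a share f = 0.2 to 0.5 of children are in such pairs; the within-family correlation of return is r = 0.5 to 1.0; the return rate p is 50%, 80% or 90%. Section 11.4 itself says that the number of co-enrolled siblings cannot be predicted.

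**Variance of one proportion.** Write v = p(1 − p). With N children there are fN/2 pairs, and each adds a covariance term 2rv to the variance of the total:

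Var(total) = Nv + (fN/2) × 2rv = Nv(1 + f × r).

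The design effect is therefore 1 + f × r.

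**Why the argument for the group difference does not transfer.** Take N/2 children per arm, equal v in both arms, and every pair split between arms. Then Cov(p1, p0) = (fN/2) × rv / (N/2)² = 2frv/N, and

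Var(p1 − p0) = 4v/N − 4frv/N = (4v/N)(1 − f × r).

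For the difference the correlation reduces the variance, so ignoring it is if anything conservative. This fits the plan's remark that the width may be inflated. For the single proportion the sign is reversed.

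**Size.** The child-level width as a fraction of the correct width is 1/√(design effect).

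- f = 0.2, r = 0.5: design effect 1.10; 1 − 1/√1.10 = 0.047, about 5% too narrow; actual coverage 2Φ(1.96/√1.10) − 1 = 93.8%.
- f = 0.5, r = 1.0: design effect 1.50; 1 − 1/√1.50 = 0.184, about 18% too narrow; actual coverage 89.0%.

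Half-widths in percentage points, from 1.96 × √(v/N) × √(design effect):

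| N | p | Child-level | Design effect 1.10 | Design effect 1.50 |
|---|---|---|---|---|
| 80 | 50% | 11.0 | 11.5 | 13.4 |
| 80 | 80% | 8.8 | 9.2 | 10.7 |
| 80 | 90% | 6.6 | 6.9 | 8.1 |
| 100 | 80% | 7.8 | 8.2 | 9.6 |

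At N = 80 the effective sample size falls to 80/1.10 = 72.7 or 80/1.50 = 53.3.

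**Schedule.** Sections 6.2 to 6.4 agree with one another and with the Day 0 to Day 56 period in 4.1: hand out at Day 0, collect and hand out at Day 28, collect at Day 56. Returns are thus due at Day 28 and Day 56. The Appendix I row fits neither simple reading. If its marks mean handing out, the Early Discontinuation mark has no purpose. If they mean collection, the Day 0 mark has none and Day 56 is missing. A table-reading error is unlikely, because the Food Frequency Questionnaire row has its only mark at Day 56, in line with 6.4.

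**The case against.** The strongest reply is that nothing turns on this interval. The objective is exploratory and descriptive, with no success threshold, test or sample size, and clustering leaves the per-child proportion unbiased. That stands, and it sets the weight of the point. It is also right that each child has a diary, so a per-child rate is a legitimate feasibility measure. Counting families instead would change the quantity being estimated.

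The size can be challenged too. Neither f nor r is in the documents. A reader might infer that one parent completes the diaries of all siblings, which would put r near 1. The documents say only that parents fill in the cards, so a shared caregiver is a reasonable inference and no more, and the range above starts at r = 0.5. With few co-enrolled siblings the effect would be negligible.

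On the schedule, a reader might infer that half of the diary data would be lost because Appendix I has no Day 56 mark. The documents do not support that. Section 6.0 describes the appendix as a summary of the evaluations in section 6, and 6.4 states the Day 56 collection outright. A reader might also object that Day 0 is a visit at which nothing can be returned. Since the measure is completion and return, the natural reading is the return visits, and this is a matter of wording only.

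**Conclusion.** The point holds, and it is minor. The planned interval for diary completion treats siblings as independent. The plan's only justification for ignoring siblings concerns the group difference and does not apply to a single proportion. With positive within-family correlation the interval is too narrow by the factor 1/√(1 + f × r): about 5% to 18% for f = 0.2 to 0.5 and r = 0.5 to 1.0. All four limits are assumptions, as is the restriction to pairs. At 80 children and an assumed 80% return rate, this moves the half-width from 8.8 points to between 9.2 and 10.7.

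Separately, Appendix I and section 6.4 disagree about Day 56. This is one table entry to reconcile. It does not show that the analysis fails to match the visit procedures, which do support a return rate at Day 28 and at Day 56.

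**What to change.** In section 11.4, keep the per-child proportion, name Day 28 and Day 56 as the return visits, and say what the overall figure means (for example, both diaries returned). Compute each 95% interval with a family-clustered (robust) variance. At N = 80 the assumed range leaves 72 families (8 pairs and 64 single children) to 60 families (20 pairs and 40 single children), enough clusters for this method.

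In Appendix I, reconcile the Food Diary row with section 6.4 and state whether a mark means handing out or collecting.

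The cost is one table row and one or two sentences, and a slightly wider interval. No new data are needed: sibling status must already be known for the allocation in section 4.1 and only has to be carried into the analysis file as a family identifier.

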12.0 OBTAINING INFORMED CONSENT

12.1. Informed Consent Prior to Research Interventions

This protocol, the informed consent document, and any subsequent modifications will be reviewed and approved by the IRB.

The informed consent will describe the purpose of the study, the procedures to be followed, and the risks and benefits of participation. The consent discussion will take place in a private room and an opportunity to ask questions will be given. A copy of the signed consent form will be given to the participant. The consent process will be documented in the research record.

All research participants who meet eligibility criteria regardless of gender or minority status are fully eligible to participate in this study.

12.2. Consent at Age of Majority

Age of majority does not apply to this protocol since only children between the ages of 2 to 8 years old will be eligible for study participation. Participation should only last approximately 56 days so participants will not reach the age of 18 before completing the study.

APPENDIX I: SCHEDULE OF EVALUATIONS

Study Visit	Screening	1 st Vaccine Visit ^a	2 nd Vaccine Visit	Follow-Up Visit (Off-Study)	Early Discontinuation
Study Day (Window)	-10 ^a	0	28 (+3 days)	56 (+/- 7 days)	
Clinical Evaluations					
Informed Consent	X				
Randomization ^d		X			
Medical History	X	X	X	X	X
Current Medication Use	X	X	X	X	
Socio-Demographics Questionnaire	X				
Food Frequency Questionnaire				X	
Compensation (\$50)	X	X	X	X	X
Laboratory Evaluations					
Blood Sample Collection ^c	X	X	X	X	X
Vaccine and Vitamin Administration					
Vaccine Administration		X ^b	X ^b		
Vitamin A and D or Placebo Administration ^d		X	X		
Participant Diaries					
Food Diary		X	X		X

^a Day 0 (1st Vaccine Dose) must occur within 10 days of screening.

^b Participants will be observed for 30 minutes post-vaccination.

^c Serum for Vitamin and Immunologic Studies

^d Randomization must occur prior to initiating any Day 0 visit evaluations.

APPENDIX II: CLINICAL AND RESEARCH TESTS

No tests and/or evaluations are performed for good clinical care.

All tests and/or evaluations are research tests.

APPENDIX III: TOXICITY GRADING TABLES

A. Division of Microbiology and Infectious Diseases (DMID) Pediatric Toxicity Tables

<https://www.niaid.nih.gov/LabsAndResources/resources/DMIDClinRsrch/Documents/dmidpedtox.pdf>
